5.1 STUDY PROCEDURES

We propose an extended 91-day, outpatient, prospective, single-center, randomized (1:1 ratio and stratified by presence of depression), double-blind, placebo-controlled, adequately powered trial of the effects of BUSP for irritability (defined primarily by observer-rated NPI Irritability domain score) in individuals with TBI of > 6 months duration. Dosing will start at 15 mg daily and will be titrated up as needed to 60 mg daily in divided doses. On Day 8 the dose will automatically increase to 30 mg daily. Dose will be further adjusted upwards at Visits 2 and 3 if observer-rated NPI-Irritability domain score has not decreased by 80% of the baseline score (if decreased by 80% the current dose will be maintained). Four outcome assessment sessions will be conducted: Day 0 (Screening/ Baseline), Days 35 and 63 (interim evaluations), and Day 91 (final outcome). After completion of the final visit, the participants will be tapered off BUSP and offered a 1-month supply of BUSP (30 -45 mg/day) to allow them to determine if they would like to ask their physician to continue to prescribe it.

Treatment and Testing Timeline

	Randomized Controlled, Double-Blind Trial Days 1 -91				Days 92- 100	Days 101-131
Visit 1: Baseline testing	Visit 2 (Day 35): Interim testing & possible dose increase	Visit 3 (Day 63): Interim testing & possible dose increase	Visit 4 (Day 91): Final testing		Taper off	Open Label

Double-Blind Study Drug Administration and Dosing Timeline

	Days 1-7 (starting dose)	Days 8-35	Days 36-63	Days 64-91	Days 92- 100 (taper)	Days 101-131 (open-label)
Treatment Group N = 37	One 5mg BUSP pill three times daily (tid) (15 mg/day)	Two 5mg BUSP pill tid (30 mg/day)	Three 5mg BUSP pill tid (45 mg/day)	Four 5mg BUSP pill tid (60 mg/day)	Decrease dose every 3 days by 15 mg	BUSP 5 mg tid. After 1 week, two 5 mg tid
Placebo Group N = 37	1 placebo pill three times daily	2 placebo pills three times daily	3 placebo pills three times daily	4 placebo pills three times daily	Decrease dose every 3 days	BUSP 5 mg tid. After 1 week, two 5 mg tid

Dosing schedule assumes less than 80% improvement in NPI-Irritability domain score from baseline to listed assessment time point. If at least 80% improvement, the dose would not be increased at that visit.

Outcome Variables:

Primary Efficacy Measure

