Dosing Adjustments: For all participants, treatment will start at a total daily dose of 15mg BUSP or equivalent placebo, and increased automatically one week later to 30mg total daily dose or equivalent placebo tablets. If observer-rated NPI-Irritability score has decreased by at least 80% of the baseline score at either Visit 2 and 3 assessments then the dose will stay at the present dose. At the Day 91, visit the participant will be provided 9 days of tapering Study Drug and a 30-day supply of open-label BUSP. On Day 92, the participant will begin tapering off the study drug by decreasing to the next lowest dose every 3 days. On Day 101, they may start open label use. Further specifics regarding dose adjustments will be outlined in the Manual of Procedures. This dosing schedule is also depicted below:

Dose Adjustment Schedule

Visit X = Day on Study Drug	<80% improved observer NPI from baseline to visit X	≥80% improved observer NPI from baseline to visit X
Day 1	15 mg daily or placebo equivalent	15 mg daily or placebo equivalent
Day 8	30 mg daily or placebo equivalent	30 mg daily or placebo equivalent
Day 36	45 mg daily or placebo equivalent	30 mg daily or placebo equivalent
Day 63	45 mg daily (or placebo equivalent) if ≥80% improved from baseline to visit 2 60 mg daily (or placebo equivalent) if ≤80% improved from baseline to visit 2	30 mg daily (or placebo equivalent) if ≥80% improved from baseline to visit 2 45mg daily (or placebo equivalent) if ≤80% improved from baseline to visit 2
Day 92	Begin taper	Begin taper
Day 101	15 mg daily	15 mg daily
Day 108	30 mg daily	30 mg daily

The above dosing schedule assumes that no changes in dose were made due to side effects or toxicity. BUSP has very few side effects and usually side effects will diminish within 3-4 days. Participants will be advised to notify the research staff if adverse changes are noted. When intolerable adverse events (AEs) occur, participants will be

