Formulation, Packaging, & Labeling: Generic buspirone hydrochloride will be used for the study. The placebo and active tablets will be identical in appearance and packaging and contain the same inactive ingredients. Pills will be dispensed in a pill bottle labeled appropriately with administration instructions, subject number, and emergency contact. To enhance compliance, the participants will be offered a pill dispenser box to help them lay out their medications for each week. We have found that such strategies are important for clinical trials involving individuals with TBI and cognitive impairment. Participants will be provided an additional 10 days of study drug to allow continued medication in unusual cases of not being able to come in during the treatment window. Participants will be asked to return any unused medication at each Study Visit. A 9-day supply of compound will be provided upon Day 91 for the purpose of weaning subjects from study medication on days 92-100. A 30-day supply of open-label BUSP will also be provided on day 91. Participants will be instructed that after taking all of the study drug taper supply, they may start the open label portion.

Storage: Designated research personnel are responsible for dispensing and accounting for all study compounds and exercising accepted medical and pharmaceutical practices. Records will be kept on inventory and dispensing record forms. Study compounds will be stored in a locked cabinet and used only as directed in this protocol.

Data Collection: Data are obtained primarily through participant and observer interviews and review of available medical records. The same interview sequence will be used each time.

Data Management: All data will be recorded on the case report form (CRF). The CRF and source data (labs, vitals, exams, adverse events) from each study visit will be reviewed by a study investigator for clinical significance and signed off. An online database using REDCap (Research Electronic Data Capture) will be developed and maintained by our Database Manager. Using a unique password, staff will run weekly data checks to allow for prompt data quality management, and generate monthly data completeness reports for discussion at monthly meetings of the investigators and RA with more frequent communication as needed.

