• Review medication instructions and dosing
• Advance drug dose (60 mg/day) unless prevented by adverse event or improved $\geq 80\%$ on NPI-I
• Remind of next study visit
• Instruct to bring in any remaining study medication to the next study visit
Calls 9, 10, and 11 (Days 70, 77, and 84 +/- 3 days):
• Inquire about number of pills taken and any problems encountered, record adverse events, record any change in concomitant medications
Visit 4 (Day 91- 3 or + 7 days): Final Outcome Visit in-person or via telephone
• Record number of remaining pills
• Collect unused medication
• Record any change in concomitant medications
• Record adverse events
• Vital signs*****
• Administer assessment measures to observer about individual with TBI: NPI & NPI-D Irritability & Agitation Domains, GIC, SASNOS, AIIM, Summary Questionnaire
• Administer assessment measures to participant about self: NPI & NPI-D Irritability & Agitation Domains, TBI QOL Anger, AIIM, PHQ-9, GAD-7, GIC, WAI-SR, Summary Questionnaire
• Record WAI-SR
• Record Clinical Global Impressions
• Ask if they think they have been receiving placebo or BUSP
• Encourage subject to make clinical appointment with rehabilitation physician for routine care and continued management, including addressing irritability as needed.
• Give subject 1-week supply of tapering dose BUSP and 1 month supply of open-label BUSP
Call 12 (Day 131 +/- 7 days): Final Safety Call
• Inquire about any problems encountered during taper and open label and record adverse events
• Complete Study Completion Form

Summary of Measures and Who Will Respond:

Measure	Buspirone Study	Measurement Study	Observer	Participant	Clinician	Research Assistant
NPI & NPI-D Aggression	X	X (observer)	X	X		
NPI & NPI-D Irritability	X	X (observer)	X	X		
SASNOS	X	X	X			
TBI-Quality of Life-Anger	X	X		X		
Personal Health Questionnaire (PHQ-9)	X			X		
Generalized Anxiety Disorder (GAD-7)	X			X		
Aggression & Irritability Impact Measure (AIIM)	X	X	X	X		
PTSD Checklist Civilian (PCL-C)	X			X		
Glasgow Outcome Scale Extended (GOS-E)	X			X (or best source)		
Clinical Global Impressions (CGI)	X				X	
Global Impression of Change (GIC)	X		X	X		
Working Alliance Inventory-Short Revised (WAI-SR)	X	X		X		X

Schedule of Events:

Procedure	Baseline Visit 1	Calls***	Visit 2 Day 35 (-3 or + 7)	Visit 3 Day 63 (+/- 3 days)	Visit 4 Day 91 (-3 or + 7)
Informed consent	X				
Screen for eligibility criteria	X				
Past medical history	X				
Vital signs *****	X		X	X	X

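### The Visit 4 taper supply (1 week) and the narrative open-label dose (30-45 mg/day) contradict the protocol's own dosing schedule

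*Combined protocol and SAP*

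**What the plan says.** **Taper supply.** The Visit 4 list in section 5.1 (Study Sequence) instructs staff: "Give subject 1-week supply of tapering dose BUSP and 1 month supply of open-label BUSP". Three other places in section 5.1 disagree:

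- Dosing Adjustments says that at Day 91 "the participant will be provided 9 days of tapering Study Drug", with the taper made by "decreasing to the next lowest dose every 3 days" from Day 92 and open label allowed from Day 101.
- Formulation, Packaging, & Labeling says: "A 9-day supply of compound will be provided upon Day 91 for the purpose of weaning subjects", and names Days 92-100.
- Both timelines show the taper on Days 92-100. The active-arm row of the dosing timeline reads "Decrease dose every 3 days by 15 mg", and the placebo row has a matching step-down.

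**Open-label dose.** The opening narrative of section 5.1 says that after the taper participants will be "offered a 1-month supply of BUSP (30 -45 mg/day"). The dosing timeline gives both arms one 5 mg tablet three times daily for a week, then two tablets three times daily. The Dose Adjustment Schedule agrees: 15 mg daily from Day 101 and 30 mg daily from Day 108.

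**The concern.** These are operative lines: one tells staff what to hand over at Visit 4, and the other states the dose of a supply that goes home with the participant. A checklist is what staff have in front of them at the visit, so a wrong figure there can reach participants even when the narrative is right.

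On the taper, someone who ends on 60 mg/day and receives one week's supply cannot complete the step-down that the protocol prescribes. The Study Sequence lists no contact between Visit 4 and the safety call on Day 131, so a short supply might not be noticed at the time. The line also names BUSP, although placebo participants taper placebo and the blind is still in force; Dosing Adjustments uses the neutral term.

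On open label, the narrative and the tables give different doses and no text says which governs. This bears most on placebo participants, for whom open label is the first exposure to buspirone.

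**Working it through.** **Taper: inputs** (all from section 5.1)

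- End dose on the default path, with less than 80% improvement at both interim visits: 60 mg/day (dosing timeline).
- Step: 15 mg down every 3 days, starting on Day 92 (dosing timeline; Dosing Adjustments).
- Tablet strength: 5 mg, so tablets per day = daily dose / 5.
- Assumption: a 1-week supply is the first 7 days of the taper schedule.

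**The protocol's 9 days reproduced.** From 60 mg/day the taper doses are 45, 30 and 15 mg/day. Three steps x 3 days = 9 days. Days 92 to 100 inclusive are 100 - 92 + 1 = 9 days. The two agree.

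**Tablets from 60 mg/day**

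| Days | Dose | Tablets |
|---|---|---|
| 92-94 | 45 mg/day | 3 x 9 = 27 |
| 95-97 | 30 mg/day | 3 x 6 = 18 |
| 98-100 | 15 mg/day | 3 x 3 = 9 |
| Total | | 54 |

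Seven days cover Days 92-98: 27 + 18 + 3 = 48 tablets. The shortfall is 54 - 48 = 6 tablets, which is 2 days (Days 99-100) at 15 mg/day or placebo equivalent.

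**Other end doses**

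- From 45 mg/day: 30 then 15 mg/day, 6 days, 18 + 9 = 27 tablets. One week is enough.
- From 30 mg/day: 15 mg/day, 3 days, 9 tablets. One week is enough.

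The checklist figure therefore fails only for participants who end on 60 mg/day. That is the protocol's default path, but the documents do not allow the number of such participants to be derived.

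**Open label: the texts side by side**

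| Source in 5.1 | First week | Afterwards |
|---|---|---|
| Opening narrative | starting dose not given | 30-45 mg/day |
| Dosing timeline | 3 tablets x 5 mg = 15 mg/day | 6 tablets x 5 mg = 30 mg/day |
| Dose Adjustment Schedule | 15 mg/day (Day 101) | 30 mg/day (Day 108) |

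A dose of 45 mg/day would need 9 tablets a day, and neither table ever reaches that. Under the tables, a 30-day supply is 7 x 3 + 23 x 6 = 159 tablets.

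**The case against.** The best defence is that the intended taper is not in doubt. Nine days appears in the narrative, in the packaging text and in both timelines, against one checklist line. That stands, and it is why the correction is easy. It does not make the checklist line right.

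The practical consequence is also small. Every participant leaves Visit 4 with open-label buspirone, so an active-arm participant who goes straight on to it has no untreated gap, whether it starts at 15 or at 30 mg/day. The documents describe no harm from missing two days at the lowest taper dose. This too stands. The reserve stock does not settle the matter, however: "Participants will be provided an additional 10 days of study drug to allow continued medication in unusual cases" refers to late visits, and unused drug is collected at Visit 4.

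Three stronger readings are tempting and are not supported:

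- *Open label would start on Day 99.* The packaging text says that "after taking all of the study drug taper supply, they may start the open label portion", and 7 days would end on Day 98. But the same paragraph sets the supply at 9 days, and Dosing Adjustments fixes Day 101. An early start requires ignoring both.
- *The open-label supply would be 21 to 111 tablets too small.* This compares 159 with 30 x 6 = 180 and 30 x 9 = 270, and so assumes 30-45 mg/day from the first day. The narrative sentence does not say that. It can be read as a target range reached after the tables' first week, in which case only the 45 mg upper end conflicts.
- *The Visit 3 bullet, which names only 60 mg/day, orders a jump from 30 to 60 mg/day.* This would concern a participant held at 30 mg/day at Visit 2 who is below 80% improvement at Visit 3. The Dose Adjustment Schedule gives 45 mg/day for exactly that case. The bullet is shorthand for the default path, as is the Visit 2 bullet.

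**Conclusion.** Two lines are wrong or unreconciled as written; the severity is minor.

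1. The Visit 4 checklist contradicts the 9-day taper stated elsewhere. From 60 mg/day it is 2 days (6 tablets) short; from 45 or 30 mg/day it is sufficient. Those left without active drug are active-arm participants who end on 60 mg/day and do not go straight to open label. This rests on the first step down falling on Day 92 and on a week meaning 7 days of the schedule.
2. The narrative open-label dose conflicts with both tables, at least at its 45 mg upper end. Two tables against one sentence favour the tables, but only the sponsor can confirm which was meant.

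A reader might infer a threat to the trial's conclusions. The documents do not support that: both items fall after the Day 91 outcome visit and leave the primary analysis, sample size and alpha untouched.

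**What to change.** - **Visit 4 checklist (5.1, Study Sequence):** change the taper item to *9-day supply of tapering study drug (BUSP or placebo)* and leave the open-label item as it is. Participants ending on 45 or 30 mg/day will use 6 or 3 of the 9 days.
- **Opening narrative of 5.1:** once the sponsor confirms that the tables govern, replace the bracketed dose range with *15 mg/day for 1 week, then 30 mg/day*. If 30-45 mg/day was intended, both tables and the supply count must change instead.
- **Optional wording:** have the Visit 3 bullet refer to the Dose Adjustment Schedule rather than name a single dose.

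The cost is a short amendment to two lines (three with the optional one), one sponsor confirmation, and a check that the Manual of Procedures and the dispensing instructions agree.

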Demographics	X				
Brief physical examination	X				
Pregnancy test for females*	X				
Laboratory tests: Serum creatinine and AST and ALT laboratory *	X				
Neuropsychiatric Inventory	X		X	X	X
TBI-QOL Anger	X		X	X	X
SASNOS	X		X	X	X
AIIM	X				X
PHQ-9	X		X	X	X
GAD-7	X		X	X	X
PCL-C	X				
GOS-E	X				
Clinical Global Impressions	X		X	X	X
Global Impression of Change			X	X	X
Working Alliance Inventory-Short Revised (WAI-SR)					X
Summary Questionnaire (Subject)					X
Summary Questionnaire (Observer)					X
Record concomitant meds	X	X	X	X	X
Study Completion Form*****		X			
Assign study number**	X				
Randomization**	X				
Review proper medication use**	X	X	X	X	X
Dose adjustment**		X	X	X	X
Dispense drug**	X		X	X	X
Pill count**			X	X	X
Record adverse events**		X	X	X	X

* These steps only performed if meets all eligibility criteria up to that point

** These steps only performed if meets all eligibility criteria

*** Calls weekly

**** Complete after telephone call 131

***** Optional

Drug Accountability: Compliance is enhanced through pill organizers, medication diaries, and frequent contacts (weekly contact). In the event that study personnel learn that a subject has not complied with the dosing schedule, the RA will try to resolve any concerns and encourage continuation in the study taking all doses as prescribed. The lack of compliance will be recorded on the relevant drug accountability case report form (CRF) for that subject.

Compliance: Pill counts will be performed at each visit. Compliance will be considered at least 75% medication consumption. If study medication compliance is at least 75% and not more than 125% over the course of the entire study, this will be considered compliant and would not represent a protocol deviation.

6.1/2 REPORTING OF ADVERSE EVENTS OR UNANTICIPATED PROBLEMS INVOLVING RISK TO PARTICIPANTS OR OTHERS

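### The final safety call is fixed to study Day 131 ± 7 while dosing runs from Visit 4, so a compliant site can close follow-up before the last open-label dose

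*Combined protocol and SAP*

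**What the plan says.** All references are to the combined protocol and SAP, section 5.1 unless stated.

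- **Contacts.** In the Study Sequence, the last weekly calls are "Calls 9, 10, and 11 (Days 70, 77, and 84 +/- 3 days"), followed by "Visit 4 (Day 91- 3 or + 7 days): Final Outcome Visit in-person or via telephone". The next and last entry is "Call 12 (Day 131 +/- 7 days): Final Safety Call". Its tasks are "Inquire about any problems encountered during taper and open label and record adverse events" and completing the Study Completion Form.
- **Taper.** Formulation, Packaging, & Labeling states: "A 9-day supply of compound will be provided upon Day 91 for the purpose of weaning subjects from study medication on days 92-100". The Visit 4 task list instead reads: "Give subject 1-week supply of tapering dose BUSP and 1 month supply of open-label BUSP".
- **Open label.** The same formulation paragraph provides a 30-day supply at Day 91 and adds: "Participants will be instructed that after taking all of the study drug taper supply, they may start the open label portion". The dosing timeline gives open-label buspirone to both arms over Days 101–131, with a dose step after one week. The Dose Adjustment Schedule places that step at Day 108.
- **Other safety routes.** Section 6.1/2 says that all adverse events in the study are recorded, that participants are encouraged to report them, and that a study pager is maintained. A footnote to the Schedule of Events says calls are weekly and gives no end day.
- **Duration.** Section 8.1 gives 131 days of participation, including open label.

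**The concern.** The call that closes safety follow-up is counted in study days, while the dosing it is meant to cover is counted from Visit 4. The two clocks part when Visit 4 is late. Even when Visit 4 is on time, the minus-7-day allowance lets the call come before the supply runs out. Adverse events in the last days of open label can then fall after the final scheduled query and after the completion form.

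The second issue is the gap before that call. In the blinded phase the starting dose and first step are followed by calls at Days 7, 14, 21 and 28. The open-label phase repeats that start and step with no listed contact, although it is the placebo arm's first buspirone in the trial. A single query weeks later depends on recall, in a population for whom the protocol itself plans aids because of cognitive impairment. The protocol also says side effects usually fade within 3–4 days, so short-lived events are the ones most easily lost.

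**Working it through.** This is day-count arithmetic.

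**1. The plan's own total.** Blinded Days 1–91 (91 days) + taper Days 92–100 (9) + open label Days 101–131 (31) = 131, which agrees with section 8.1. A 30-day supply started on Day 101 ends on Day 101 + 29 = Day 130, one day short of the timeline header.

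**2. Call window.** 131 − 7 = Day 124; 131 + 7 = Day 138; 138 − 124 + 1 = 15 permitted days.

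**3. Last dose and call days before it.** Last dose = Visit 4 day + taper days + 30. Call days strictly before it = last dose − 124.

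| Visit 4 | Taper supply | Last dose | Call days before it (of 15) |
|---|---|---|---|
| Day 88 | 9 days | Day 127 | 3 |
| Day 91 | 9 days | Day 130 | 6 |
| Day 98 | 9 days | Day 137 | 13 |
| Day 88 | 7 days | Day 125 | 1 |
| Day 91 | 7 days | Day 128 | 4 |
| Day 98 | 7 days | Day 135 | 11 |

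Every row leaves at least one compliant call day before the last dose. With Visit 4 on Day 98 and a 9-day taper, even a call on the nominal Day 131 is 137 − 131 = 6 days early.

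**4. Time with no scheduled query** (earliest / nominal / latest call)

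- From a Day 91 visit: 124 − 91 = 33, 131 − 91 = 40, 138 − 91 = 47 days. Across the Visit 4 window the extremes are 124 − 98 = 26 and 138 − 88 = 50.
- From the first possible open-label dose on Day 101: 23, 30, 37 days. If open label moves with Visit 4 (start = Visit 4 + 10), the extremes are 124 − 108 = 16 and 138 − 98 = 40. With a one-week taper and an on-time visit, the start is Day 99 and the gap is 25 to 39 days.
- From the Day 108 dose step: 16, 23, 30 days.

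**The case against.** The best defence has four parts.

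- **At nominal timing the call works.** Day 131 follows a Day 130 last dose. That is correct, and a count of permitted days is not a probability that the call will be early. The defect is that the stated window allows it.
- **The late-visit case assumes that dosing moves with Visit 4.** The Dosing Adjustments paragraph names Days 92 and 101 without saying what happens after a late visit. But both supplies are given at Visit 4, open label follows use of the taper supply, and spare study drug is provided for late attendance. A shift is the natural reading. The on-time case does not need it.
- **Other safety routes exist.** Participants are told to report problems, a pager is kept, unresolved events are followed, and further detail is left to a Manual of Procedures that is not in these documents. A reader might infer that the placebo arm goes unmonitored on buspirone for 33–47 days. That is not supported: the interval starts at Day 91, the placebo arm tapers placebo pills until Day 100, and what is missing is a scheduled query, not every route of reporting.
- **The weekly-call footnote may cover this period.** It has no end day, so it is ambiguous. The itemised sequence lists no call between Days 84 and 131.

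The effect on the main results is also limited. The primary endpoint is read at Day 91, and section 8.1 names no analysis of the open-label period.

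**Conclusion.** The point stands as a gap in adverse event collection after Day 91. A fully compliant final call can precede the last open-label dose by up to 6 days with an on-time Visit 4 and up to 13 days with Visit 4 on Day 98 (4 and 11 days with a one-week taper supply). No query is scheduled between Visit 4 and that call. For the placebo arm this means 23 to 37 days from a Day 101 first dose.

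These figures assume that the taper starts the day after Visit 4, that open label follows at once, and that both supplies are taken in full. Open label is optional and has no latest start date, so a delayed start would move the last dose later.

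Three stronger readings are tempting but unsupported:

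- **First lifetime exposure to buspirone.** Section 3.1 excludes use in the month before enrollment, allergy and prior failed response, so other past users may enter. It is the first in-trial exposure only.
- **A forecast number of missed events.** The adverse event rates quoted in section 2.0 come without a dose or time frame, and open-label uptake is unknown.
- **A contradiction because no taper is described when open label ends.** The documents do not require one, and the supply is meant to help participants decide whether to ask their physician to continue.

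**What to change.** 1. Anchor Call 12 to the last open-label dose, or to the last taper dose for those who decline open label, for example 0 to +7 days after it and with no negative window. Complete the Study Completion Form only after that call.
2. Reconcile three sets of statements: the taper supply (9 days in Dosing Adjustments and in Formulation, Packaging, & Labeling; one week in the Visit 4 list); the open-label length (a 30-day supply; Days 101–131 in the timeline); and the weekly-call footnote (the numbered call list stops at Day 84 and resumes only with Call 12).
3. Optionally, add one short call near the open-label dose step, using the adverse event question already scripted for Call 2. It could also record the actual open-label start date, which helps to time Call 12.

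**Cost.** Items 1 and 2 are protocol wording and use a call that already exists. With an on-time Visit 4 and a 9-day taper, the re-anchored call falls on Days 130–137, inside the present window. With Visit 4 on Day 98 it falls on Days 137–144, so follow-up ends at least 137 − 131 = 6 days past the stated 131 and at most 144 − 138 = 6 days past the latest call now allowed. The participation statement in section 8.1 would need a matching edit. Item 3 costs one short call per participant.
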